3.8.5.2. State-Trait Anger Expression Inventory-2 (STAXI-2)

The STAXI-2 assesses various areas of anger and the traits of experiencing anger. The 57 item assessment with a 4-point score (“Not at all” to “Almost Always”) includes three sections or scales, State Anger (subscaled S-Ang, S-Ang/F, S-Ang/V, and S-Ang/P), Trait Anger (T-Ang, Tang/T, and T-Ang/R), and Anger Expression and Anger Control (AX-O, AX-I, AC-O, AC-I, and AX Index). For each scale

and subscale, raw scores and percentiles are calculated based on the four point score for each item. At each time point of the baseline and each visit after treatment and during follow-up, mean and standard deviation, as well as median and interquartile range, of each scale/subscales raw scores and will be summarized by the treatment groups (Table 3.8.15a-b). The raw scores and percentile for each scale/subscale at the baseline, end of each treatment block, and end of every four week follow-up time will be tested between the two treatment groups using SAS PROC GLM at each visit. A mixed regression model will be used to test the main effects of treatment using SAS PROC MIXED. The model will include visit, treatment and treatment by visit interaction adjusted for the baselines. The percentiles of each scale are categorized into $\leq 25\%$, $>25\%$ to $<75\%$, and $\geq 75\%$. At each time point of the baseline and each visit after treatment and during follow-up, numbers and percentages of each scale/subscales percentile for each category, as well as clinical evaluation trigger (i.e. $\leq 25\%$ and $\geq 75\%$) are tabulated by the treatment groups (Table 3.8.16). the difference of each category and trigger for each scale/subscale at each visit between the treatment groups will be tested using Pearson χ^2 or Fisher exact test, whichever it applies. The overall differences across all visits for each scale between the treatment groups will be tested by generalized linear mixed model using SAS PROC GLIMMIX.

3.8.6. Drug Abuse and Alcoholism Tests

3.8.6.1. Drug Abuse Screening Test (DAST)

The DAST is designed to provide a brief instrument for clinical screening drug abuse. This 28 self-report item questionnaire uses 'yes' or 'no' responses to address various problems related to drug misuse, and yields quantitative scores ranging from 0 to 28 with a higher score endorsed in the direction of increased drug use problems. A score of 5 or higher is indicative of a possible drug use disorder. the test is performed at screening, end of acute treatment, and end of follow-up. The number and percentage of each item will be tabulated by the treatment groups at each measurement time (Table 3.8.17). the difference of each item at each visit between the treatment groups will be tested using Pearson χ^2 or Fisher exact test. At each time point, summary statistics of DAST scores will be tabulated (Table 3.8.18) and tested

between the two treatment groups using SAS PROC GLM at each measurement adjusted for the baseline. A mixed regression model will be used to test the main effects of treatment using SAS PROC MIXED. The model will include visit, treatment and treatment by visit interaction adjusted for the baselines. Further the test scores will be dichotomized into < 5 and ≥ 5 as indication of drug use. The logistic regression will be used test the difference between the treatment groups using PROC LOGISTIC and the overall differences across all visits for each scale between the treatment groups will be tested by generalized linear mixed model using SAS PROC GLIMMIX (Table 3.8.19).

3.8.6.2. Michigan Alcoholism Screening Test (MAST)

The MAST is parallel self-administered items on the DAST and is a widely used assessment device for alcoholism. This 25 self-report item questionnaire uses 'yes' or 'no' responses to provide screening for clinical and non-clinical settings, and yields quantitative scores ranging from 0 to 50 with a higher score endorsed in the direction of increased alcoholism. the test score is usually categorized into 0-3 (no apparent problem), 4 (early or middle problem drinker), 5-50 (problem drinker/alcoholic). The test is performed at screening, end of acute treatment, and end of follow-up. The number and percentage of each item will be tabulated by the treatment groups at each measurement time (Table 3.8.20). the difference of each item at each visit between the treatment groups will be tested using Pearson χ^2 or Fisher exact test. At each time point, summary statistics of DAST scores will be tabulated (Table 3.8.21) and tested between the two treatment groups using SAS PROC GLM at each measurement adjusted for the baseline. A mixed regression model will be used to test the main effects of treatment using SAS PROC MIXED. The model will include visit, treatment and treatment by visit interaction adjusted for the baselines. Further the test scores will be dichotomized into 0-3, 4 and 5-50 to assess severity of alcohol drinking. The logistic regression will be used test the difference between the treatment groups using PROC LOGISTIC and the overall differences across all visits for each scale between the treatment groups will be tested by generalized linear mixed model using SAS PROC GLIMMIX (Table 3.8.22).

3.8.7. Urine Toxicology Screening and Alcohol Test

Urine rapid toxicology screening for drug and alcohol test is performed at screening phase, acute treatment phase of blocks 2, 4, and 6, taper phase week 2, and follow-up phase of weeks 4, 12, and 20. The test includes five drugs on dip card A: methamphetamine (MET) and ecstasy (ECS), amphetamine (AMP) and methylenedioxyamphetamine (MDA), marijuana (THC), cocaine (COC), and opiates (OPI); five drugs on dip card B: barbiturates (BAR), benzodiazepines (BZD), phencyclidine (PCP), methadone (MTD), and oxycodone (OXY); and alcohol. All test results are recorded as negative, positive, and no results. At each testing time point, the number and percent of each category of the testing results will be tabulated (Table 3.8.23), and the difference between the treatment groups will be tested using Pearson χ^2 test.

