2.5 Study Assessments Used in the Analysis

2.5.1. Basic Information

Participants' demographics, medical history, physical exam, laboratory, toxicology, pregnancy test and medication use are collected.

2.5.1.1 *Demographics/Medical History/Laboratory/Toxicology/Medication Use.*

Relevant demographics are collected as to age, gender, racial/ethnic grouping, military history and income. In addition, a standard medical history and physical examination are completed as well as laboratory tests including a complete blood count (CBC), electrolytes (chemistry), thyroid panel and a liver function test. An alcohol test and urine drug toxicology screen are conducted prior to randomization and also randomly during the following time points of study participation: a) acute treatment phase: 2nd, 4th, and 6th (if still in acute treatment) weeks ; b) taper phase: 2nd week; c) follow-up phase: 1st, 3rd, and 5th months.

2.5.1.2 *Physical Exam*

A physical exam of the oral cavity, head, eyes, ears nose and throat, cardiovascular system, lungs, abdomen (liver/spleen), extremities, skin, neuropsychiatric mental status and sensory/motor status, musculoskeletal system and general appearance will be performed during the screening/baseline phase and at week 9. Height will be recorded during the screening/baseline phase only.

2.5.1.3 *Pregnancy Test*

A pregnancy test is conducted on all female patients of childbearing potential (that is, all women except for those who are post menopause for > 2 years or who have a history of hysterectomy or surgical sterilization) prior to randomization and every four weeks during the study. Information on medication use (prescription, natural food products, and "over the counter") will be collected at screening and updated after each block of five sessions during the treatment phase and every four weeks during the follow-up phase.

2.5.1.4. *Antidepressant Treatment History Form (ATHF)*

The ATHF provides a uniform and rigorous method of eliciting and recording a patient's past experience using antidepressant medications (Sackeim et al., 1990). The

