2.5.1.5 Concomitant medications

All medications taken by the subject during the screening/baseline phase, during the treatment phase and during the follow-up phase must be pre-approved by the site PI or his/her designee whenever possible to avoid interactions with the study treatment.

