37	Adverse Events (AE) and ADE and Serious Adverse Events (SAEs) and UADE	As required														

*B= Baseline

*S= Screening

¹ Sessions 21-25 (block 5) and 26-30 (block 6) may not be required if patient goes into remission earlier

² Must be conducted within 7 days prior to randomization

³ Termination Form will be completed at the end of the study OR when a patient decides to end study participation prior to the study completion date; i.e., a patient decides to withdraw or leave the study for any reason, withdraws consent, or is suspended from the study.

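### The urine toxicology test in SAP 3.8.7 does not exclude 'no results' from the chi-square and names no Fisher option, so its p-value can reflect missing or not-due tests rather than positivity

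*SAP*

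**What the plan says.** SAP 3.8.7 covers five drug results on each of two dip cards, plus alcohol. The tests are done at screening, acute blocks 2, 4 and 6, taper week 2, and follow-up weeks 4, 12 and 20. On coding it states: "All test results are recorded as negative, positive, and no results". On analysis it states that "the number and percent of each category of the testing results will be tabulated" in Table 3.8.23 and, in the same sentence, that "the difference between the treatment groups will be tested using Pearson" chi-square.

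The section does not say which categories enter the test, does not define *no results*, and gives no alternative for sparse counts.

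Two other places bear on who is tested. Section 2.5.1.1 makes the sixth-week acute test conditional on the patient still being in acute treatment. A footnote to Appendix 5.2 says that sessions 21-25 and 26-30 "may not be required if patient goes into remission earlier". The same appendix heads the taper weeks as PRN.

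**The concern.** A comparison of toxicology results should ask whether the proportion positive differs between arms. If *no results* is a column of the table being tested, the statistic also responds to any difference in how often a result is absent. It spends a second degree of freedom on that even when absence is balanced. The first effect can produce a significant p-value with no difference in positivity. The second can weaken a real difference.

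The SAP's own schedule offers a route to unequal absence. If early remitters have no block 6 test and are coded *no results*, then an arm with more remission will show more *no results* at that time point. A treatment benefit would then appear as a toxicology difference.

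The second issue is sparse data. Individual drug rows may contain very few positives, and the Pearson approximation is least reliable there.

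**Working it through.** Section 3.8.7 states no rate, count or power, so there is no figure of its own to reproduce.

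**Inputs from the SAP.** 180 per arm (2.6); 1:1 allocation (2.3); two-sided alpha 0.05 (3.1.2); three result categories and Pearson chi-square (3.8.7); assumed remission of 6% sham and 16% rTMS (2.6). All toxicology counts below are assumptions.

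**Formula.** Chi-square = sum of (observed − expected)²/expected, without continuity correction. Three columns have 2 degrees of freedom and two columns have 1.

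**A. A difference appears without one in positivity.** Arms 161/8/11 and 143/8/29 (negative/positive/no results).
- Three columns: expected counts in each arm are 152, 8 and 20. The statistic is 2 × (9²/152 + 0 + 9²/20) = 2 × (0.533 + 4.05) = 9.17, 2 df, **p=0.010**. The positive column contributes zero.
- Valid results only: 8/169 (4.7%) against 8/151 (5.3%). The statistic is 0.053, 1 df, **p=0.82**.

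**B. A difference is weakened.** Arms 149/13/18 and 137/25/18, with absence equal at 10%.
- Three columns: expected counts are 143, 19 and 18. The statistic is 2 × (6²/143 + 6²/19 + 0) = 4.29, 2 df, **p=0.117**.
- Valid results only: 13/162 (8.0%) against 25/162 (15.4%). The statistic is the same 4.29, now with 1 df, **p=0.038**. The smallest expected count is 19, so Pearson is adequate here.

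**C. What the remission link could do at block 6.** Suppose *no results* runs at 6% and 16%, with equal positivity among those tested. The noncentrality is 180 × 2 × (0.05²/0.11 + 0.05²/0.89) = 360 × 0.02554 = 9.19, whatever the common positivity. With 2 df the three-column test rejects about 78% of the time (80% in a 20,000-run simulation at 10% positivity). The two-column test rejects 5% of the time. This borrows the remission rates as rates of absence, which overstates the effect if some patients remit only at the last block.

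**D. Sparse counts.** At an assumed 2% positivity the expected count is 180 × 0.02 = 3.6 per arm, below the usual threshold of 5. Fisher's exact test is available for adverse events (3.8.1), C-SSRS (3.8.5.1), STAXI-2 categories (3.8.5.2), DAST items (3.8.6.1) and MAST items (3.8.6.2). Section 3.8.7 names Pearson alone.

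**The case against.** The SAP does not expressly say that the test has three columns. It lists how results are recorded and then says that the arms are compared, so an analyst could run positive against negative without contradicting it. The shell for Table 3.8.23 is in an attachment that is not shown and may settle this. *No results* may mean an invalid strip rather than a test never taken. Appendix 5.2 heads its last acute column as session 30 or last, so an early remitter may have a closing test after all. Because every category is tabulated, a reader could also see a p-value driven by absent results.

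These points stand as limits on the claim. They do not remove it: the text permits two analyses that can disagree at the 0.05 level, and the plain reading is the worse one. Section 2.5.1.1 and the last-session heading leave it unclear whether early remitters are tested at that point.

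A reader might infer something stronger: that the comparison counts prescribed medicines as drug use, since card B includes "barbiturates (BAR), benzodiazepines (BZD), phencyclidine (PCP), methadone (MTD), and oxycodone (OXY"), medicines "must be pre-approved by the site PI or his/her designee whenever possible", and medication use is "updated after each block of five sessions during the treatment phase and every four weeks during the follow-up phase". The document does not support that. Section 3.8.7 compares test results and never labels a positive as drug use. Which classes patients may take, and how a positive is judged, may be set in the protocol, which is not at hand. Prescribing that is balanced by randomisation would dilute a difference, not create one. Any estimate of power lost on an any-drug positive rate needs a composite that the SAP does not define. Recoding explained positives as negative would also hide misuse of a prescribed drug.

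**Conclusion.** The point holds as a minor defect of specification in one safety table. As written, section 3.8.7 lets *no results* into the chi-square and offers no exact test. On assumed counts at 180 per arm, the choice of columns moves p from 0.82 to 0.010 in one case and from 0.038 to 0.117 in another. The actual size is unknown, because the SAP gives no rates of positive or absent results and does not say how tests that were not due are coded. Arm-dependent absence is plausible from the schedule, not shown.

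The primary endpoint, the secondary endpoints and the sample size do not use these results. The history-of-substance-abuse covariate in the primary model is taken from the SCID, so it is also untouched.

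**What to change.** In section 3.8.7 and the Table 3.8.23 shell:

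1. For each drug and for alcohol, test positive against negative among valid results only.
2. Use Fisher's exact test when expected counts are small, and Pearson otherwise.
3. Define *no results*, and report it by arm on its own line outside the test. Report tests that were not due (acute treatment ended early, no taper) on a further separate line.
4. Optionally, add a descriptive line that flags positives matching a medicine on the medication-use form (Form 15), without recoding them as negative.

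The cost is a few sentences, one revised shell and a derived not-due flag, which the treatment, taper and visit forms in Appendix 5.2 should support. The optional line needs a merge with the medication form and a mapping of panel classes to coded drug names. No new data collection is needed.

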3.9 Additional Analyses

3.9.1 Treatment effect on PTSD

3.9.1.1. PTSD Check List (PCL-M)

The PTSD checklist –military version (PCL-M) used in the study is a 17-item self-report measure reflecting DSM-IV symptoms of PTSD. It has multiple clinical and research purposes including screening individuals for PTSD, helping in diagnostic assessment of PTSD and monitoring change in PTSD symptoms. The PCL-M inquired about symptoms in response to stressful experience in military service based on the 17 items. For each item there were five scales – not at all, a little bit, moderately, quite a bit, and extremely, valued from 1 to 5. The total symptom severity score that ranged from 17-85 was obtained by summing the scores from each of the 17 items. A cutoff score of 44 or above is considered as PTSD positive. At each time point of the baseline, end of acute treatment, and end of follow-up, summary statistics of the total scores will be tabulated by treatment group (Tables 3.9.1a-c), and analyzed at each measurement time point using SAS PROC GLM adjusted for baseline; and the mixed model will be performed to test total score across time point using SAS PROC MIXED. The covariates of the model will include baseline, treatment, time point, and interaction

of time and treatment. The least square means (LS-means) and their standard errors at each visit will be plotted by treatment groups (Figures 3.9.1a-c). PTSD severity is categorized as low (17-33), moderate (34-43), and high (≥ 44) based on the PCL-M score. The number and percentage of the severity will be tabulated by the treatment groups at each measurement time (Tables 3.9.2a-c). The difference of each category at each visit between the treatment groups will be tested using Pearson χ^2 tests and logistic regression by PORC LOGISITC adjusted for the baseline. The overall differences across all time points for each severity category between the treatment groups will be tested by generalized linear mixed model using SAS PROC GLIMMIX. The model will include the baseline, treatment, time, and interaction of time and the treatment.

3.9.1.2. Clinician Administered PTSD Scale (CAPS)

The CAPS is a structured interview for assessing core and associated symptoms of PTSD. It assesses the frequency and intensity of each symptom and yields both continuous and dichotomous scores for current and lifetime PTSD symptoms. Possible scores range from 0 to 136. At each time point of the baseline, end of acute treatment, and end of follow-up, summary statistics of the total scores will be tabulated by treatment group (Tables 3.9.3a-c), and analyzed at each measurement time point using SAS PROC GLM adjusted for baseline; and the mixed model will be performed to test total score across time point using SAS PROC MIXED. The covariates of the model will include baseline, treatment, time point, and interaction of time and treatment. The least square means (LS-means) and their standard errors at each visit will be plotted by treatment groups (Figures 3.9.2a-c). PTSD severity is categorized as asymptomatic (0–19), mild (20-39), moderate (40-59), severe (60-79), and extreme (≥ 80) based on CAPS score. The number and percentage of the severity will be tabulated by the treatment groups at each measurement time (Tables 3.9.4a-c). The difference of each category at each visit between the treatment groups will be tested using Pearson χ^2 tests and logistic regression by PORC LOGISITC adjusted for the baseline. The overall differences across all time points for each severity category between the treatment groups will be tested by generalized linear mixed model using

SAS PROC GLIMMIX. The model will include the baseline, treatment, time, and interaction of time and the treatment.

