2.6 Sample Size Consideration

The primary hypothesis of the study is that in VA patients with TRMD, rTMS will result in a greater remission rate at the end of acute treatment than sham rTMS. The primary outcome measure in this study is success or failure to achieve remission from depression as defined by a score on the Hamilton Rating Scale for Depression (HRSD24) of 10 or less. The primary analysis will be done as an "intent-to-treat" analysis, i.e. patients will be analyzed in the groups to which they were randomized and drop-outs will be considered treatment failures. The primary hypothesis will be addressed using a logistic regression model with PTSD diagnosis, history of substance abuse, and site as covariates. Based on review of the studies reported in the Introduction Section, the Planning Committee felt that a 10% difference between treatments would be of clinical relevance given the severity of the illness. With a sample size of 180 per group, the proposed study will have a power of 81% to detect an absolute difference between groups of 10% in the percentage of those participants who remit (6% sham and 16% rTMS). Thus, a total of 360 patients are required. This goal of 360 patients, larger than any previous study, also provides a measure of protection should some assumptions be wrong.

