3.1.2 Analysis Conventions

This section details general policies to be used for the statistical analyses. Departures from these general policies may be given in the specific detailed sections of this statistical analysis plan. When this situation occurs, the rules set forth in the specific section take precedence over the general policies. The following policies will be applied to all data presentations and analyses.

- All statistical tests will use a significance level of $\alpha = 0.05$. Two-tailed tests will be performed for all analyses that use statistical testing.
- All p-values will be rounded to 3 decimal places. All p-values that round to 0.000 will be presented as '<0.001' and p-values that round to 1.000 will be presented as '>0.999'. Any p-value $\leq \alpha$ will be considered statistically significant.
- Summary statistics will consist of the number and percentage of responses in each category for discrete variables, and the mean, median, standard deviation (SD), minimum, and maximum for continuous variables.
- All mean and median values will be formatted to one more decimal place than the measured value. Standard deviation values will be formatted to two more decimal places than the measured value.
- All percentages will be rounded to one decimal place. The number and percentage of responses will be presented in the form XX (XX.X), where the

- percentage is in the parentheses. The decimal of the percentage may be dropped due to space constraints when creating a table.
- For a continuous variable, if it is normally distributed or approximately normally distributed, Student t test and/or the general linear regression will be performed to test the group difference as proposed in the analysis plan, otherwise, Wilcoxon test and/or a quantile regression will be used as an alternative analysis method; for a categorical variable, Pearson χ^2 test and/or a corresponding generalized linear regression will be performed to test the group difference.
 - All listings will be sorted for presentation in order of treatment group, site number, subject number, and date of procedure or event.
 - All analysis and summary tables will have the population sample size for each treatment group in the column heading.
 - Calculating change from baseline to a visit will be done as follows: change = visit –baseline.

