3.7.2.1.2. Depression Severity based on MADRS Score

According to Herrmann et al (Herrmann et al 1998), MADRS score can be categorized into four depression severity groups, i.e. normal (0-6), mild depression (7-19), moderate depression (20-34), and severe depression (>34). The severity of the depression will be tested at end of the acute treatment, and end of the following-up using proportional odds model adjusted for baseline and SAS PROC LOGISTIC will be used to run the model and p-values related to the treatment effect will be presented. Further, the generalized linear mixed model will be applied to test the differences of the proportions of subjects' remission across all the time point. The link function will be cumulative logit. SAS PROC GLIMMIX will be used to analyze the data (Tables 3.7.10a-c).

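### PTSD severity classes on CAPS and PCL-M are tested one at a time at unadjusted 0.05, unlike the SAP's other ordered severity scales, with about a 21% or 12% chance of a false-positive class per visit and test type

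*SAP*

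**What the plan says.** SAP 3.9.1.2 defines five ordered CAPS classes: "PTSD severity is categorized as asymptomatic (0–19), mild (20-39), moderate (40-59), severe (60-79), and extreme" (80 or more). SAP 3.9.1.1 defines three ordered PCL-M classes: low (17-33), moderate (34-43) and high (44 or more). Both sections then specify the same two layers of testing:

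- By visit: "The difference of each category at each visit between the treatment groups will be tested using Pearson" chi-square tests, and by logistic regression adjusted for baseline.
- Across visits: "The overall differences across all time points for each severity category between the treatment groups will be tested by generalized linear mixed model", fitted in PROC GLIMMIX. No link function is named.

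Both sections also test the total score, with PROC GLM at each time point adjusted for baseline and with PROC MIXED over time.

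On error control, SAP 3.1.2 says "All statistical tests will use a significance level of" 0.05 and "Two-tailed tests will be performed for all analyses that use statistical testing". The only tightened level, 0.01 in SAP 3.7.2.6, is for the secondary endpoints. CAPS and PCL-M are not among the five secondary outcomes in SAP 2.4.2.

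For ordered severity on the depression scale MADRS (SAP 3.7.2.1.2) the plan tests severity "using proportional odds model adjusted for baseline" and adds a mixed model with a cumulative logit link. SAP 3.7.2.2.2 (BDI), 3.7.3.1.2 (QIDS-C16) and 3.7.3.2.2 (BHS) also name a proportional-odds model and a cumulative logit link.

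**The concern.** Each class-by-class test has as its null that the share of patients in that one class is equal between arms. For an interior class this is a poor proxy for equal severity. If treatment lowers severity, patients move into the class from above and out of it below, so its share may rise, fall or stay put. Several unadjusted p-values then stand where one question was asked, and the plan does not say how to read a table in which one class is significant and its neighbours are not.

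At stake is the reading of Tables 3.9.2a-c and 3.9.4a-c. They sit under a heading about the treatment effect on PTSD and could be cited in support of such a claim. The SAP already has a suitable model for ordered severity and gives no reason for leaving it here.

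**Working it through.** **Inputs from the SAP.** Two-sided 0.05 per test (3.1.2); 180 per arm (2.6); five CAPS and three PCL-M classes (3.9.1.2, 3.9.1.1).

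**Assumptions, not in the SAP.** The class distributions, the size of any benefit, and complete data.

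**The SAP's own figure.** The only power statement concerns the primary endpoint: "With a sample size of 180 per group, the proposed study will have a power of 81"%, for "6% sham and 16% rTMS". The uncorrected two-proportion formula gives 86.1%. With the continuity correction and d = 0.10, the effective n is (180 - 1/d)²/180 = 170²/180 = 160.6, which gives about 82%. The stated figure is therefore reproduced within about a point. The SAP states no error rate or power for the PTSD severity tests.

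**Step 1: chance of a false-positive class, one visit and one test type.** If the class tests were independent:

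- CAPS: 1 - 0.95^5 = 22.6%
- PCL-M: 1 - 0.95^3 = 14.3%

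Shares within one scale sum to 1, so the tests are dependent. I therefore simulated 200,000 multinomial trials per setting, with a chi-square test of each class against the rest and, for comparison, one tie-corrected Wilcoxon test on the ordered class (the score test of the proportional-odds model).

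| Setting, no effect | CAPS, any class | PCL-M, any class |
|---|---|---|
| 180 per arm, equal classes | 21.2% | 12.5% |
| 180 per arm, skewed classes | 20.4-21.2% | 11.9-12.3% |
| 90 per arm | 19.7-20.9% | 11.5-12.3% |

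The single ordinal test rejects in 4.9-5.1%. The any-class rates hardly depend on the assumed distribution.

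**Step 2: direction of an interior class.** Apply a proportional-odds benefit of 1.5, multiplying each cumulative odds by 1.5.

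- Equal CAPS classes: cumulative shares 0.20, 0.40, 0.60, 0.80 become 0.273, 0.500, 0.692, 0.857. The moderate share goes from 0.200 to 0.692 - 0.500 = 0.192, a fall.
- Classes weighted to severe (0.10, 0.15, 0.20, 0.25, 0.30): cumulative shares 0.10, 0.25, 0.45, 0.70 become 0.143, 0.333, 0.551, 0.778. The moderate share goes from 0.200 to 0.551 - 0.333 = 0.218, a rise.

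The same benefit moves the same class in opposite directions, depending only on where the population sits.

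**Step 3: power with a real benefit.** For equal classes and odds ratio 1.5, the moderate class has difference 0.0077 and standard error √(2 × 0.196 × 0.804/180) = 0.0418, so z = 0.18. Two-sided power is Φ(-1.96 + 0.18) + Φ(-1.96 - 0.18) = 0.038 + 0.016 = 5.4%, as in the simulation. Over odds ratios 1.5 to 2.0, 180 per arm:

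| Class | Power |
|---|---|
| CAPS equal: asymptomatic / mild / moderate / severe / extreme | 37-82% / 10-14% / 5-8% / 14-34% / 30-65% |
| CAPS weighted to severe: mild / moderate / severe | 18-39% / 7-8% / 8-19% |
| PCL-M equal: low / moderate / high | 46-90% / 6-10% / 42-82% |
| PCL-M 10/15/75%: moderate | 17-39% |

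**Step 4: overall detection, CAPS equal classes.** At least one class rejects in 63-95%; the single ordinal test rejects in 58-96%. With normal scores of mean 50, SD 28 and a 0.4-SD benefit, the figures are 93% and 95%.

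**Step 5: number of tests.** With two post-baseline time points, two test types at each and one mixed model per class, the count per population is 5 × 2 × 2 + 5 = 25 p-values for CAPS and 3 × 2 × 2 + 3 = 15 for PCL-M, in each of three populations. The 21% and 12% cover only one visit and one test type, so the chance over the whole set is higher.

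**The case against.** Four points can be made for the plan.

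- **The total scores are tested.** Both sections analyse them by GLM and MIXED. For a 0.4-SD benefit and 180 per arm, a two-sample test on the score has z = 0.4 × √(180/2) = 3.79, and power Φ(3.79 - 1.96) of about 97%. This stands: the class tables supplement a direct test of severity.
- **The end classes are cumulative cuts.** CAPS 0-19 and 80 or more, and PCL-M 17-33 and 44 or more, do measure severity, and 44 is the SAP's own PTSD-positive cutoff. A reader might infer that the class tests never address lower severity, or that the middle classes cannot detect a benefit. Neither is supported: the end classes have useful power, and off-centre classes reach 14-39% in several settings. Only the central class stays near alpha, and which class that is depends on a distribution the SAP does not give.
- **The text might mean one model.** PROC LOGISTIC with an ordered outcome fits a cumulative logit by default, and SAP 3.8.6.2 is equally loose about three MAST classes. If the analyst ran one cumulative-logit model and one full-table chi-square, the 21% and 12% would not arise. This reading is possible, but it does not fit the mixed-model sentence, which specifies a test for each severity category.
- **The stakes are low.** Section 3.9 holds additional analyses, and no primary or secondary conclusion depends on these p-values. This stands and limits the weight of the point.

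**Conclusion.** The point holds as one of error control and interpretability in an additional analysis. As written, the class-by-class tests carry about a 21% (CAPS) or 12% (PCL-M) chance of at least one false-positive class per visit and test type, against 5% for one ordinal test. These figures need only the 0.05 level and the number of classes, and are stable over the distributions tried. The departure from the SAP's handling of MADRS, BDI, QIDS-C16 and BHS severity rests on no assumption.

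The power figures do rest on assumed distributions, benefits and complete data, and serve only to show that interior classes are hard to read. A reader might infer that a real PTSD benefit would be missed. The calculations do not support that: the chance that some CAPS class rejects is close to the power of the ordinal test, although part of it comes from the uncontrolled error, and the total-score analyses test severity directly. The impact is modest and confined to Tables 3.9.2a-c and 3.9.4a-c.

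**What to change.** In SAP 3.9.1.1 and 3.9.1.2, replace the class-by-class tests with:

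- one proportional-odds model for the ordered class, adjusted for baseline class, at end of acute treatment and at end of follow-up;
- one mixed model in PROC GLIMMIX with a cumulative logit link across the post-baseline visits, as in 3.7.2.1.2;
- counts and percentages by class as description, without p-values.

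The cost is SAP wording and changes to the two sets of table shells; the MADRS severity code can be reused, and neither data collection nor design changes. The downside is reliance on proportional odds, which should be checked, for instance with the score test. The change gives one test per question at each time point. It does not adjust across visits or the three populations, so the results should still be presented as additional analyses.
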